### **Procedure for obtaining informed consent**

After the initial phone screenings detailed above the post doctoral fellow will explain the purpose, procedures, and potential discomforts/risks of the study and then obtain a signed informed consent from the prospective subject.

Subjects will be paid \$25 for the Clinical Evaluation, \$150 for each MRI appointment in which they participate and \$25 for a telephone follow-up evaluation. If scanning is stopped due to subject discomfort, technical problems, or if a subject is found ineligible prior to entering the scanner, they will still be compensated for their visit.

### **Confidentiality**

To respect confidentiality and the HIPAA rules, the subject's name is not stored with their data. All the participant's identities and data will be held in confidential files. On entry to the study subjects will be assigned a study ID#, and all files will use this ID for future references. All information regarding experimental subjects will be kept in a locked file cabinet in the office of the principal investigator. All study staff are IRB certified and all information and records are in compliance with HIPAA rules.

[figure not shown]
## **V. STUDY PROCEDURES**

### **Study visits and parameters to be measured**

#### **Experimental Design Overview**

The fMRI scanning session will take approximately 90 minutes. There are 2 conditions, i.e. two scanning sessions (*note: 5 non-MDD test subjects have one scanning session only*). Both conditions will consist of one 30 minute tVNS session, one inhalation-gated the other exhalation-gated. During both

conditions, we will perform electrical stimulation to the ear, to stimulate the auricular branch of the vagus. Stimulation parameters will be identical.

[figure not shown]

## **tVNS Procedures for all Scans**

Periods of tVNS (inhalation-gated vs. exhalation-gated) stimulation will alternate with periods of rest, during which time the electrodes will remain in place.

tVNS will be performed at the left ear by either [name] (trained in tVNS) or the post-doctoral fellow. Two reusable MRI compatible electrodes will be attached to the cymba and cavum concha (**Figure 2**) of the auricle. Current will be delivered with UROstim transcutaneous electrical stimulator (Schwa Medico, Germany). Current amplitude will be set between the sensitivity threshold and the pain threshold for each subject. The waveform will consist of monophasic rectangular pulses. The stimulation parameters will include 30 Hz stimuli with 3 increased gradually to a maximum of 8 mA (in 0.25-m stimulation until a comfortable tolerance level is reached. 30 seconds during the fMRI scan runs. These stimulation used in iVNS for depression. Respiratory gating for stim respiratory cycle. An adaptive threshold detection method end-expiration in real-time and provide a signal controlling or inhalatory pahse of respiration. Correct respiratory experimenter via running chart of the respiration signal an

Since receptors respond directly to current load and normal tissue response alters electrical resistance, it is important to use a current-constant EA stimulation device. A voltage-constant device (common in clinical practice) produces variable current load, and leads to variations in stimulation intensity.

## **Figure 2 – tVNS electrode placement**

stimulation parameters will include 30 Hz stimuli with 300  $\mu$ sec pulse width. The output current will be increased gradually to a maximum of 8 mA (in 0.25-mA increments) to allow accommodation to the stimulation until a comfortable tolerance level is reached. Stimulation will be on for 30 seconds and off for 30 seconds during the fMRI scan runs. These stimulation parameters and procedures are similar to those used in iVNS for depression. Respiratory gating for stimulation will require real-time evaluation of the respiratory cycle. An adaptive threshold detection method will be employed to detect end-inspiration and end-expiration in real-time and provide a signal controlling the delivery of the stimuli during the exhalatory or inhalatory phase of respiration. Correct respiratory-gated stimulation will be confirmed by the experimenter via running chart of the respiration signal and stimulus pulse.

## Clinical Assessments

Outcomes will include whether acute stimulation with tVNS reduces mood symptoms. Our group has found tVNS diminishes anxiety in an acute paradigm. Measures at intake will include: Structured Clinical Interview for DSM Disorders, Hamilton Rating Scale for Depression 17, and the Montgomery Asperger Depression Rating Scale. Before and after tVNS/fMRI, we will assess mood with the Beck Depression Inventory-II, Hamilton Rating Scale for Depression 17, Spielberger State-Trait Anxiety Interview, and a Visual Analog Scale.

## **Blood Draw**

Our on-site Phlebotomist will draw one sample [(approximately 5 teaspoons (26 ml)] at the beginning and another blood sample [approximately 3 teaspoons (13 ml)] after each of the two imaging visits. Previous studies from our group have demonstrated gonadal hormonal regulation of mood and autonomic nervous system circuitry. In addition, a significant body of evidence has suggested an interrelationship between the activity of the autonomic nervous system, particularly the vagus nerve and the immune system. We will use estradiol, progesterone, cytokines (IL-1 $\beta$ , IL-6, IL-10, TNF $\alpha$ ), and C-reactive protein (CRP) levels as covariates in the analysis of tVNS effects in the activation of brain regions related with mood and autonomic modulation. The results of the blood tests are not clinically relevant to individual persons; therefore, we will not return results to the subject. However, when the study analyses are complete, we will make study results available to the subject, if desired (although individuals are not identified in these analyses).

## **Saliva Collection**

We would like to collect a sample of saliva (15 ml saliva tube) to examine cortisol levels in order to evaluate the state of the hypothalamic-pituitary-adrenal (HPA)-axis in depressed subjects. Collection will take place the evening before the scan (11pm), prior to the scan, and 60 minutes following the picture task. This variable will be considered in the analysis of the effects of our intervention in the modulation of the stress response circuitry and central autonomic network. The samples will have no personal identifying information and will be placed in a storage bank in secure buildings in the Boston medical area that have limited access. They will be used only for research that is carefully reviewed and approved both by this study and the Institutional Review Board.

## **Scanning**

Subjects will be randomized as to the order of scan dates (inhalation-gated vs. exhalation-gated), which will be separated by at least one week. Scanning begins with the subject at full rest then they will undergo our mild visual stress paradigm for 18 minutes. Then the electrodes will be placed. The stimulation block will have a total duration of 30 minutes. The electrodes will be withdrawn at 20 minutes after and the mild visual stress task repeated. Patients will first undergo a mild stress task where they view pictures during fMRI scanning. Our fMRI stress paradigm has been described in detail previously and conducted in healthy subjects, MDD, and psychotic cases. Briefly, subjects view 3 stimulus blocks (6 images per block) for 30 seconds (1 image every 5 seconds) in the following order: fixation, neutral, and negative images (see definitions below). Subjects view this sequence 4 times during each of 3 runs for a total of 72 images (24 images per condition per run), and press a button each time a new image appears in order to ensure attention to the images, without adding cognitive load. Images were drawn from the International Affective Picture System (IAPS) according to affective valence and arousal (negative = unpleasant + high arousal, neutral = neutral + low arousal). Fixation images are based on Fourier transformations of each neutral image to create an image with the same physical properties of the original but without recognizable content. The stress task will be repeated after the tVNS portion of imaging. When the fMRI session is complete, subjects will be shown two blocks of negative and neutral images sampled from the set shown during imaging and will be asked to provide subjective ratings of arousal using the Self-Assessment Manikin (SAM).

## **Post-Scan Follow Ups**

After each fMRI scan we will follow up with each subject to assess their mood. We will follow up one day and seven days after each scan. The follow-ups one day after the scan will consist in the administration of a Visual Analogue Scale for mood states through a REDcap online survey. For the 7th day follow-ups we will administer the Hamilton Depression Scale, Beck Depression Inventory-II, Spielberger State-Trait Anxiety Interview, and the Visual Analog Scale. The first 7th day follow up will be conducted in person at Imaging Visit #2. The second 7th day follow up will be conducted by phone. These follow ups will evaluate acute changes in mood following tVNS administration during the imaging visits.

## **Acquisition Parameters for fMRI and Physiological Data Collection**

General MRI Scanning Procedure for Subjects: When the subject arrives for the MRI scan, she will be asked to fill out a brief questionnaire in order to confirm that they can safely enter the MRI scanner. She will be asked to remove any metallic items from her body and may be given non-metallic shirts and pants to wear in the scanning room. The participants will be instructed to lie on the MRI table. Once the participant is positioned comfortably on the MRI table, the table will be moved into the MRI scanner tube. The participant will be able to communicate with the operator outside of the MRI room. The participant will be asked to lie still during imaging. To help immobilize the participant's head, foam pillows will be placed under and around the head. Subjects may be asked to use a "bite bar" which conforms to the teeth, or a plastic mask that conforms to the face, to help keep the head still. Since the MRI scanner makes loud knocking or beeping sounds during the scan, the participant will be asked to wear earplugs during imaging. If the participant becomes uncomfortable at any time, the scan will be stopped and the problem eliminated. If it is not possible to alleviate the problem the scan will be stopped and the participant will be free to discontinue participation.

Structural MRI: To provide anatomical localization of the functional signal, high-resolution (voxel size= 1 mm^3) structural MRI scans will be acquired using a T1-weighted MP-RAGE pulse sequence (TR= 2300 ms, TE= 2.95 ms, acceleration= GRAPPA factor 2, flip angle= 9°, FOV= 256 x 256 mm^2, 176 axial slices).

BOLD imaging: Whole-brain fMRI data will be acquired with gradient-echo echo-planar imaging (EPI) using Simultaneous Multi-Slice (SMS) acquisition with multi-band factor 5 (TR= 1250ms, TE= 33 ms, flip angle= 65°, FOV= 200 x 200 mm^2, 75 axial slices, voxel size= 2 mm^3).

Physiological Monitoring During fMRI Scanning: Peripheral physiological data will be acquired using a Powerlab system (ML880; ADInstruments Inc, Colorado Springs, CO) at a 1000 Hz sampling rate. We will use a magnetic resonance-compatible pneumatic belt placed around the subject's lower thorax to evaluate changes in respiratory volume. In addition, cardiac pulsatility data will be acquired using a piezoelectric pulse transducer (AD instruments Inc., Colorado Springs, CO) attached to the right index finger.

## **Data Storage**

Any data obtained from subjects during this study will not leave our institute in any form that would identify individual subjects. All subject data will be identified by a subject ID number. The PI will keep a master list of subject names and corresponding subject ID numbers in a locked cabinet at the BWH. Electronic data will be housed in secure, password protected computer accounts.

## **VI. BIOSTATISTICAL ANALYSIS**

### **Specific data variables being collected for the study**

For this study data will be collected from MRI in electronic form. Subjects will also provide data in the form of questionnaires related to mood and medical history. Copies of these subject forms/questionnaires are included with this application.

### **Sample Size (Power Analysis)**

The present study will recruit a total of 20 subjects (women age 25-40 with recurrent MDD). This will allow for the possibility of unusable data due to subject motion during scanning, scanner artifact problems as well as problems with the collection of behavioral data and human error.

Group size power statistics: In a previous study of manual acupuncture (N = 11), we were able to detect changes in activation of limbic and subcortical gray structures in the approximate range of -0.7% to -0.2%.

Also based on previous data (amygdala, manual acupuncture stimulation), we will assume a standard deviation of BOLD signal change of 2.5% for the purpose of power calculation and sample size determination. We do not consider temporal autocorrelation in the power calculations that follow, though we will take autocorrelation into account during the data analysis.

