## **II. SPECIFIC AIMS**

Major Depressive Disorder (MDD) is a leading cause of morbidity and mortality worldwide. Abnormalities in vagal tone are more common in MDD, particularly loss of parasympathetic cardiac regulation, and increase the risk for cardiovascular disease (CVD). Vagal nerve stimulation (VNS) is an FDA approved treatment for MDD that modulates circuitry implicated in mood regulation. However it is unclear whether therapeutic benefit of VNS on mood, can also reduce cardiac morbidity and mortality. The circuits for autonomic cardiac regulation overlap with those for mood regulation, but modulation of ANS has not been directly associated with mood response. As a first step, we will identify whether VNS effects on mood circuitry in MDD are associated with modulation of vagal tone and mood.

In the proposed study in MDD patients, we will 1) identify the neural circuitry associated with tVNS, 2) identify its acute effects on heart rate variability, and 3) assess the impact of brain activity and ANS function on mood. We will control for factors known to impact vagal tone, in particular gonadal hormones in women. This is the first study to map the neurobiology of mood and vagal response to VNS using a less invasive form of VNS that may have a wider application.

**Specific Aim 1:** To determine the acute effects tVNS on cerebral blood flow in MDD patients.

Hypothesis 1: During real tVNS/fMRI interleaving, tVNS will deactivate amygdala, parahippocampal gyrus, hippocampus, posterior cingulate, and precuneus and will activate insula, thalamus and anterior cingulate.

Hypothesis 2: Brain activity deficits in stress response circuitry in MDD will be attenuated following 20 minutes of tVNS, in hypothalamus, amygdala, hippocampus, and anterior cingulate gyrus.

**Specific Aim 2:** To determine the acute effects of tVNS on vagal tone and mood in MDD patients.

Hypothesis 1: tVNS will increase high frequency R-R variability and decrease mood symptoms compared to baseline.

**Specific Aim 3:** To compare the effects of exhalation-gated tVNS with inhalation-gated tVNS on cerebral blood flow, vagal tone and mood regulation in MDD patients.

Hypothesis 1: Exhalation-gated tVNS will have a significant greater impact on regulation of cerebral blood flow, vagal tone and mood in MDD patients compared to inhalation-gated tVNS.

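### The power inputs describe a stimulation-evoked BOLD change that Section VI never tests, so Aim 1 Hypothesis 1 gets no activation result and N = 20 is not derived

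*Combined protocol and SAP*

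**What the plan says.** Section VI, Sample Size (Power Analysis), plans for 20 women with recurrent MDD. Its effect range comes from an earlier manual-acupuncture study of 11 subjects, in which "we were able to detect changes in activation of limbic and subcortical gray structures in the approximate range of -0.7% to -0.2" per cent. The SD has a similar source, earlier amygdala data from the same kind of stimulation, and the plan states it thus: "we will assume a standard deviation of BOLD signal change of 2.5% for the purpose of power calculation and sample size determination". On serial dependence, the section adds: "We do not consider temporal autocorrelation in the power calculations that follow". No calculation follows, and no alpha, target power or unusable-data rate is given.

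Section II sets two imaging hypotheses under Aim 1:

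- **Hypothesis 1** concerns the stimulation period itself: "During real tVNS/fMRI interleaving, tVNS will deactivate amygdala, parahippocampal gyrus, hippocampus, posterior cingulate, and precuneus". It also predicts activation of insula, thalamus and anterior cingulate.
- **Hypothesis 2** concerns the stress-task response after stimulation compared with before, "in hypothalamus, amygdala, hippocampus, and anterior cingulate gyrus".

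Aim 3 compares exhalation-gated with inhalation-gated stimulation.

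Section VI, Magnetic resonance imaging data analysis, specifies one activation analysis: negative versus neutral images, in a two-factor model of time (PRE, POST) and session. Mean betas from each significant cluster then enter a regression on BDI change. The stimulation runs appear only in the functional connectivity analysis.

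**The concern.** The acupuncture inputs are stimulation-evoked signal changes in limbic structures, and the quoted changes are negative. In kind and sign they fit Aim 1 Hypothesis 1. Section VI does not analyse that effect, and the picture-task contrasts that it does analyse have different precision.

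Three things are at stake. The first hypothesis of the first aim has no planned activation test, although the stimulation runs are scanned. A reader cannot tell what 20 participants can detect for any imaging aim. And the link between stress-circuit activity and mood is examined only where a group-level cluster passes the threshold, although a brain-mood association across participants does not need a group-mean effect.

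**Working it through.** **1. Can 20 be reproduced?** The plan gives no alpha or power, so assume two-sided 0.05 and 80% power, with n = (SD × (1.960 + 0.842) / effect)².

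- SD 2.5% between subjects: n = 101 for 0.7% and 1,227 for 0.2%.
- SD 2.5% per volume, on-off contrast (subject-level SD 0.132%, step 3): n = 1 for 0.7% and 4 for 0.2%.

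Neither gives 20. With alpha and power unstated, 20 can be neither reproduced nor called wrong.

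**2. Which SD?** The plan does not say. The autocorrelation sentence suggests a per-volume SD, since autocorrelation arises only among repeated volumes within a subject. Steps 3 and 4 take that reading as an assumption.

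**3. Within-subject variance of each contrast** (independent volumes).

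- TR is 1.25 s (Acquisition Parameters). Picture blocks last 30 s, and "Subjects view this sequence 4 times during each of 3 runs" (Scanning). Volumes per image condition per task: 3 × 4 × 30 / 1.25 = 288.
- "Stimulation will be on for 30 seconds and off for 30 seconds during the fMRI scan runs" (text under Figure 2). Over the 30 minutes given in Scanning, that is 900 / 1.25 = 720 volumes on and 720 off. Over the 20 minutes given in Aim 1 Hypothesis 2, it is 480 each. The two durations must be reconciled.
- On-off, one session: 2 × 2.5² / 720 = 0.01736, SD 0.132% (20 minutes: 0.02604, SD 0.161%).
- Negative minus neutral, one task: 2 × 2.5² / 288 = 0.0434.
- POST minus PRE, averaged over two sessions: (2 × 0.0434) / 2 = 0.0434, SD 0.208%.
- PRE/POST by session interaction: 4 × 0.0434 = 0.1736, SD 0.417%.

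Ratios to the one-session on-off variance: 0.0434 / 0.01736 = 2.5 for session-averaged PRE/POST and 0.1736 / 0.01736 = 10 for the interaction. With 20 minutes they are 1.7 and 6.7.

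**4. Power at N = 20 for an assumed 0.2% effect**, one-sample t on the subject-level contrast, 19 df, two-sided 0.05 (critical value 2.093). The noncentrality is 0.2 × √20 / SD = 0.894 / SD, where SD² = within-subject variance + (between-subject SD of that contrast)². The documents give no between-subject SD; 0 is the best case and 0.5% is an assumption.

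| Contrast | SD at 0 | Power | SD at 0.5% | Power |
|---|---|---|---|---|
| On-off, one session, 30 min | 0.132% | about 100% | 0.517% | 38% |
| PRE/POST, session-averaged | 0.208% | 98% | 0.542% | 35% |
| PRE/POST by session | 0.417% | 53% | 0.651% | 26% |

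If 2.5% is instead the between-subject SD of a contrast, power at N = 20 is 6.3% for 0.2% and 22.1% for 0.7%.

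**5. What N = 20 can detect, free of the SD question.** For a within-subject contrast at 80% power (noncentral t), the detectable effect in units of the contrast's own SD is:

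| Usable N | Two-sided 0.05 | Two-sided 0.0125 (0.05 / 4 regions) |
|---|---|---|
| 20 | 0.66 | 0.81 |
| 16 (assumed) | 0.75 | 0.93 |

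**The case against.** A reader might go further and infer that the study was sized on the wrong contrast and is underpowered by a factor of 10. The documents do not support that, for these reasons:

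- **No calculation links the inputs to 20**, so the plan cannot be said to have been sized on them.
- **The factor of 10 belongs to one term.** The interaction answers Aim 3. Aim 1 Hypothesis 2 is a PRE/POST effect, where the ratio is 2.5 and best-case power for 0.2% is 98%. The 10 also depends on the comparator: it is 5 against the exhalation-minus-inhalation difference in on-off response and 20 against the on-off effect averaged over sessions. Between-subject variance shrinks it.
- **The BDI regression is not confined to interaction clusters.** The text takes every significant cluster of a model that also has main effects of time and session. An empty regression is a risk, not an expectation.
- **The acupuncture effect sizes are not estimates for the picture task.** Applying 0.2% there only illustrates precision. Power of the cluster-level FWE test cannot be computed from the documents.
- **The plan already restricts testing to a priori regions** with small-volume correction, and its connectivity-mood regression states no significant-cluster condition.

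All of this stands, and it limits the size of the point. It does not supply the missing on-off analysis, the announced calculation or a definition of the SD, and it does not remove the significance condition on the activation-BDI regression.

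**Conclusion.** The point holds in four parts that rest on the text alone. The power inputs fit Aim 1 Hypothesis 1, but Section VI has no activation test of it. The announced calculation is absent and N = 20 is not derived. The 2.5% SD is undefined. The activation-BDI regression depends on a cluster passing.

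The numbers are conditional on a per-volume SD of 2.5%, independent volumes, all 20 usable and the timings above. On those assumptions, the tested contrasts have 2.5 times (PRE/POST) and 10 times (interaction) the within-subject variance of the on-off contrast; the second figure is 6.7 with 20 minutes. Power for 0.2% runs from 98% down to 35% for PRE/POST, and from 53% down to 26% for the interaction, as the assumed between-subject SD goes from 0 to 0.5%. That omitted SD largely decides the answer, so neither adequate nor inadequate power can be claimed from the plan. The connectivity regression is not affected.

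**What to change.** Keep N at up to 20.

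1. **Add the missing test.** In Section VI, specify a stimulation-on versus stimulation-off BOLD contrast in the regions named in Aim 1 Hypothesis 1, per session and averaged over sessions.
2. **Remove the significance condition from the BDI regression.** Run it for all participants on mean betas over the four regions of Aim 1 Hypothesis 2 (hypothalamus, amygdala, hippocampus, anterior cingulate), using the POST-minus-PRE change, whether or not a cluster is significant. Keep the adjustment for baseline BDI and antidepressant use, and keep the voxel-wise region-of-interest analysis as planned.
3. **Complete or delete the power statement.** Define the 2.5% SD as per-volume or between-subject and tie the acupuncture inputs to the on-off contrast. Replace the announced calculation with the detectable standardised effects in step 5 of the working, or delete the statement.

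This needs no extra participants, scans or data: one more first-level contrast and a changed regression predictor. The downsides are a little more analysis work, possible dilution of a focal effect by a region mean, and a less favourable statement of sensitivity.
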